Traditionally eradication efforts of *S. aureus* colonization have focused on removing colonization in the anterior nares (nose) and skin. A recent investigation by our group found that among persons with an *S. aureus* SSTI and their household members, the most common site of colonization of *S. aureus* on the human body is not the anterior nares, but the oropharynx (26% vs. 24%), with overlap of colonization far from universal. In fact, 50% of oropharyngeally colonized persons were not nasally colonized. Other investigations show a similar magnitude of *S. aureus* oropharyngeal colonization. There are mounting data that decolonization regimens that ignore the pharynx are not effective at preventing recurrent *S. aureus* SSTIs. However, prospective data on oropharyngeal decolonization of *S. aureus* in children are lacking.

We hypothesize that suboptimal *S. aureus* prevention efforts stem from previous inattention to eradication of *S. aureus* oropharyngeal colonization. To this end, we will conduct a clinical trial on eradication of oropharyngeal *S. aureus* colonization. Data from our "proof of principle" study will form the foundation of more comprehensive efforts to prevent recurrent *S. aureus* infections in children.

We will perform a prospective, double blind, randomized controlled clinical trial of 0.12% chlorhexidine (CHG) oral rinse versus placebo oral rinse for children age 5-17 with *S. aureus* oropharyngeal colonization. We hypothesize that, compared to placebo, 0.12% CHG rinse will reduce oral *S. aureus* colonization. We choose CHG given its wide availability, excellent safety profile, and low cost. We will enroll 240 children who have a history of *S. aureus* infection or SSTI in the prior year. Consenting subjects will be screened for *S. aureus* oropharyngeal colonization using a rapid molecular test. Subjects will be eligible if they have *S. aureus* oropharyngeal colonization during a screening visit, are able to gargle, and can be followed for 28 days. CHG oral rinse will be used twice daily for 7 days total.

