- Receipt of systemic antibiotics in the prior 28 days.
- Plans for administration or likely receipt of systemic antibiotics in the next 28 days (e.g., if the patient suffers from recurrent infections such as otitis media or has a planned surgery that requires prophylactic antibiotics).
- Plans for hospitalization or likely hospitalization in the next 28 days (e.g., if the patient suffers from recurrent infections).
- Any of the following in the prior 6 months: hemodialysis, peritoneal dialysis, central venous catheter placement, and systemic chemotherapy for cancer, any immunocompromising condition. These criteria ensure that subjects enrolled with have CA-*S. aureus* infections and are likely colonized with USA300 *S. aureus*, the most common cause of SSTIs in the U.S.
- Previous participation in the study.

All patients who participate in the clinical trial will be followed for 28 days for the purpose of determining which subjects achieve and maintain eradication. Participants will be enrolled regardless of race, ethnicity, or gender. While younger children commonly suffer from SSTIs, for this investigation we will only enroll children 5 years of age and older, as younger children may not be able to gargle. In a pilot study of 64 children from a general dentistry practice asked to gargle, among the 12 children ages 3-4, only 2 (17%) could complete a 30 second gargle, whereas 51/52 (98%) of those ages 5-8 could gargle successfully ([name], personal correspondence).

To recruit subjects, study coordinators will screen the PED three times daily. During screening, they will

Baseline visit

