Participants will be asked to come to the research clinic 7 days after initiation of oral CHG, i.e., at the end of their treatment (Visit 2). A subsequent visit will occur at 28 days (Visit 3). The purpose of these visits is to ascertain oropharyngeal eradication of *S. aureus* both short term (primary study outcome) and longer term. Based on previous investigations conducted at our center(s), we estimate a 10% attrition rate.^{75,77,78,81,82} At Visit 2, participants will be swabbed the nares and oropharynx for the presence of *S. aureus* and to complete a follow-up survey about any recurrent infections, new medical history, or receipt of antibiotics. At Visit 3, participants will return to the research clinic to complete a follow-up survey. Study staff will also call all subjects remind them of their upcoming study appointments and at days 14 and 21 to address any questions the participant or their parent/guardian may have about the study. Adverse events will be measured at each scheduled and unscheduled (see below) follow-up visits. Adverse events will be measured using the Medical Dictionary for Regulatory Activities Terminology (MedDRA) version 14.0 or later terms.

Unscheduled visits

If participants or their parent/guardian experience potential adverse drug events that occur during the follow up period, subjects or their parent/guardian will be encouraged to contact study staff. If the event may be of clinical concern, the event will be referred to a study physician and the oral rinse discontinued, if applicable. If deemed necessary by the study physician or the subjects' primary physician, participants will be asked to return to the research clinic for evaluation by a study investigator.

Aim 1: Determine the efficacy of oropharyngeal decolonization among children suffering from CA-MRSA and other *S. aureus* skin infections

To determine if oropharyngeal *S. aureus* colonization can be eradicated, we will perform a prospective, double blind randomized controlled clinical trial of 0.12% oral chlorhexidine (CHG) oral rinse versus placebo for children age 5-17 with *S. aureus* oropharyngeal colonization. We hypothesize that 0.12% CHG rinse will

reduce oral *S. aureus* colonization better than placebo treatment. The findings from this Aim will provide “proof of principle” data on the ability of oral antiseptics to eradicate oropharyngeal *S. aureus* colonization in children.

Power and Sample Size

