Given this investigation is minimal risk, Data and Safety Monitoring (DSM) will be performed by the Investigative Team. DSM will be performed according to standards of The Eunice Kennedy Shriver National Institute of Child Health and Human Development (NICHD) Policy for Data & Safety Monitoring.⁹¹ These will include reviewing monthly summaries of the number of patients enrolled, age, ethnic and gender makeup, Number of patients retained in the study, number of dropout and lost to follow up, adverse events (AEs), and serious adverse events (SAEs) (See Aim 2, below for further details). Subjects that report treatment related adverse events will discontinue the oral rinse and come to the research clinic for an unscheduled visit.

Aim 2: Assess the safety, tolerability, and compliance of oropharyngeal decolonization among children and their caregivers. We will administer a detailed and systematic survey of side effects, tolerability and compliance of the oropharyngeal decolonization regimen to determine the effects, concerns, and usability of this regimen in children for both the child participants and their parents/caregivers. Findings will identify adverse effects and barriers to use to be considered when possibly administering this regimen in the future.

Data Analyses

Adverse events will be coded to a Medical Dictionary for Regulatory Activities Terminology (MedDRA) version 14.0 or later terms. Verbatim description and the MedDRA System Organ Class and Preferred Term for all adverse events will be contained in the subject data listings. A separate listing sorted

by MedDRA System Organ Class and Preferred Term will include all verbatim descriptions associated with the Preferred Terms.

Data for adverse events will be analyzed using the treatment-emergent signs and symptoms philosophy.

Treatment emergent signs and symptoms are defined as adverse events where:

- onset occurs during exposure to study medication or within 7 days after the last dose of study medication, having been absent prior to receiving study medication, or
- onset reoccurs during exposure to study medication or within 7 days after the last dose of study medication, having been present but stopping prior to receiving study medication, or
- worsening in severity occurs during exposure to study medication relative to the pre-treatment state, when the adverse event is continuous.

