All reported adverse events (regardless of treatment-emergent or not) will be included in a by-subject adverse event listing. Only treatment-emergent adverse events will be included in summary tables. The number of subjects (incidence) of treatment-emergent adverse events will be presented as well as the frequency of all adverse events reported.

Summary tables of adverse events will include the following:

- Summary of adverse events by severity and relationship
- Summary of related adverse events
- Summary of Serious adverse events
- A listing of any on-study pregnancies

Percentages of subjects who reported adverse events will each be compared separately among each group using Chi-Square or Fisher Exact tests, as appropriate.

Aim 3: Determine the *S. aureus* genetic backgrounds associated with breakthrough oropharyngeal colonization.

Advances in sequencing technologies and the availability of large computing power and bioinformatics have allowed WGS to become the method of choice to characterize emerging phenotypes.⁷² WGS also allows examination of the relationship between presence of the *qac A/B* gene in *S. aureus* at baseline and treatment response. WGS allows detection of this plasmid-based resistance gene for comparative analysis among a subset of *S. aureus* isolates from our population, as described below.

We will molecularly characterize all baseline *S. aureus* isolates and “breakthrough” (failure) isolates using whole genome sequencing (WGS) for identification of breakthrough *S. aureus* isolates. We will compare breakthrough isolates with baseline nasal and oropharyngeal isolates to determine if breakthrough isolates represent either: a) recolonization with the original oropharyngeal isolate, b) recolonization with the baseline nasal isolate, or c) acquisition of a new *S. aureus* strain. Additionally, we will investigate whether *S. aureus* associated with treatment failures have acquired or possess the *qac A/B* gene.

Sample Size

Data Analyses

WGS will be done in the laboratory of [name] (see Letter of Support), using established techniques.^{92,93} [name] lab has ample experience performing WGS on *S. aureus* and other bacterial pathogens.⁹²⁻⁹⁴ [name] lab will also supply analytic support to assist with interpretation of findings.

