All subjects who have consented will have the rapid *S. aureus* test performed with results shared with the subject's parent/guardian, the subject, and the clinician, if approved by the parent/guardian. Study staff will educate and the subject's parent/guardian, and subject (if of sufficient age), the clinical significance of the results, either positive or negative. More specifically, they will be educated that currently testing for *S. aureus* oropharyngeal colonization is considered experimental and that if the test is positive, the clinical significance is unclear. They will also be educated that tens of millions, perhaps over 100 million Americans are colonized in the throat with *S. aureus*, and the vast majority do not suffer consequences of having this bacteria live in the throat. Upon request, subjects will be provided with a written copy of their results as well as a written description of the clinical significance of oropharyngeal colonization that they can share with their provider, if they wish.

Subjects with a positive screening test will undergo 3 study visits total: baseline/enrollment visit (Visit 1), Day 7 (Visit 2), and Day 28 (Visit 3). Consenting subjects will have their anterior nares and oropharynx swabbed at Visits 1, 2, and 3. A survey will be administered at the initial visit and a follow-up survey will be administered at Visits 2, and 3. The survey administered at Visit 1 will collect information about demographics, medical history, and behavioral risk factors for skin and soft tissue infection and colonization. Subjects will be randomized to 0.12% CHG oral rinse or placebo use for 7 days. All subjects will receive educational materials regarding *S. aureus* and skin infections and their prevention. Those randomized to the intervention will receive additional verbal and written information on use of CHG oral rinse. The survey administered at Visit 2 will collect information about the adherence, tolerability, and adverse events during the intervention period. The survey administered at Visit 3 will collect information about (late) adverse events, changes in household dynamics and individual behavior (e.g., hygiene) that may affect results of Visit 3 nasal and oropharyngeal colonization studies.

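### Adverse events are collected to Day 28, but the summary tables, including the one for serious events, stop 7 days after the last rinse, and worsening stops counting at the last rinse

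*Combined protocol and SAP*

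**What the plan says.** The rinse period is short: "CHG oral rinse will be used twice daily for 7 days total" (Scientific Abstract). Follow-up is longer: "All patients who participate in the clinical trial will be followed for 28 days" (Inclusion and Exclusion criteria). Collection of safety data spans the whole of it. Under Follow-up visits, "Adverse events will be measured at each scheduled and unscheduled (see below) follow-up visits", and under Human Subjects/Investigational New Drug, "The survey administered at Visit 3 will collect information about (late) adverse events". Visit 3 is at Day 28.

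The Data Analyses section of Aim 2 defines treatment-emergent events by three criteria. The first is new onset: "onset occurs during exposure to study medication or within 7 days after the last dose of study medication". The second, recurrence of something that had stopped before treatment, carries the same 7-day extension. The third, for continuing events, is narrower: "worsening in severity occurs during exposure to study medication relative to the pre-treatment state". It has no extension past the last dose.

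The same section then sets the reporting rule: "Only treatment-emergent adverse events will be included in summary tables". The tables it names include "Summary of Serious adverse events". Three further provisions bear on the point:

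- Every event, treatment-emergent or not, goes into a by-subject listing.
- The frequency of all reported events is promised alongside treatment-emergent incidence.
- The percentages of subjects reporting events are to be compared between arms by Chi-square or Fisher's exact test, and that sentence is not limited to treatment-emergent events.

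**The concern.** Safety and tolerability form a specific aim of the trial, and the plan presents the findings as the counterweight to any benefit. The randomized placebo arm makes the adverse-event data interpretable, and the tables are where a reader will look for the contrast.

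The table rule cuts off before data collection does. A serious event three weeks after randomization would be recorded, coded and listed, yet it would be missing from the table meant to summarise serious events. A reader of that table would not know it was incomplete.

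The worsening criterion adds a smaller inconsistency. In the week after the last rinse, a new symptom is tabulated, but an existing one that starts to worsen is not. The plan gives no reason for treating the two differently.

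**Working it through.** The plan states no end day for the window, so there is no figure of its own to reproduce. The end day follows from its definitions. The sample size plays no part in this point.

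**Inputs**
- Treatment: 7 days (Scientific Abstract).
- Extension for onset and recurrence: 7 days after the last dose. Extension for worsening: none (Aim 2, Data Analyses).
- Follow-up: 28 days (Inclusion and Exclusion criteria).

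**Formulas**
- Window end = day of last dose + 7.
- Days outside the tables = 28 − window end.

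| Last dose | Window ends | Days outside | Share of 28 days |
|---|---|---|---|
| Day 2 (early stop) | 2 + 7 = 9 | 28 − 9 = 19 | 68% |
| Day 6 | 6 + 7 = 13 | 28 − 13 = 15 | 54% |
| Day 7 (full course) | 7 + 7 = 14 | 28 − 14 = 14 | 50% |
| Day 8 | 8 + 7 = 15 | 28 − 15 = 13 | 46% |

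The plan does not number the dosing days, so a full course may end on Day 6, 7 or 8 depending on the convention. Day 7 is used below.

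**The three criteria side by side, full course**

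| Event | Begins Day 5 | Begins Day 10 | Begins Day 20 |
|---|---|---|---|
| New onset | tabulated | tabulated | listing only, under the table rule |
| Recurrence | tabulated | tabulated | listing only, under the table rule |
| Worsening of a continuing event | tabulated | listing only, under the table rule | listing only, under the table rule |

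Serious events follow the same rows, because the serious-event summary is one of the named tables and no exception is made for it.

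**Does another sentence restore the late events?** There are two candidates.

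1. The promised frequency of all reported events could mean every event to Day 28, or all occurrences within the treatment-emergent set. The text does not settle which.
2. The between-arm test could cover all events or only treatment-emergent ones. If all, the test and the tables use different event sets. If only treatment-emergent, late events are not tested.

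Under the wider reading of either sentence, late events enter an overall count or comparison. Under no reading do they enter the serious-event summary.

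**Dependence on stopping.** Data Analyses and Data and Safety Monitoring has subjects who report treatment-related events stop the rinse. The window is tied to the last dose, so it closes sooner for those children. If such stops were more common in one arm, that arm would be tabulated over a shorter period. The documents give no stopping rates, so the size of this cannot be stated.

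**The case against.** A window of last dose plus 7 days is an explicit, prespecified choice for a 7-day topical course, and events starting weeks later are more likely to be background. Nothing is lost from the record: all events are listed by subject, and the monthly safety review covers adverse and serious adverse events with no treatment-emergent limit. With about 60 randomized children, a late serious event would be noticed. Visit 3 collection does not itself contradict the table rule either. The preceding scheduled visit is at Day 7, so Visit 3 is also the first scheduled visit to pick up events from Days 8-14, which are inside the window.

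Most of this stands. The window is defensible as the main analysis, and extending it to Day 28 would be a change of convention rather than a correction. But listings and monthly review serve oversight. They do not make the reported serious-event table complete.

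Two stronger readings are tempting and should not be drawn:

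- **That Aim 2 cannot compare late events between arms.** The test sentence is not restricted to treatment-emergent events, and a frequency of all reported events is promised, so such a comparison is not ruled out.
- **That half of all events are lost.** That would need onset to be uniform over 28 days. No figure in the documents supports this, and effects of a rinse used for 7 days need not be spread that way.

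**Conclusion.** The point holds in a limited form and is minor. As written, events starting more than 7 days after the last rinse are left out of the summary tables, including the serious-event summary, although they are collected to Day 28. Worsening that begins in the week after the last rinse is also left out, while onset and recurrence in that week are counted. Worsening during exposure is tabulated and is not affected.

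The size is 14 of 28 follow-up days for a full course with the last dose on Day 7, and 19 of 28 after a last dose on Day 2. These are shares of calendar time. The number of events affected cannot be estimated from the documents. The conclusion rests on reading the table rule literally and on taking the serious-event summary as one of the tables it governs.

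The gain from a correction lies in complete display more than in testing. With 30 children per arm (60 randomized ÷ 2) and no events on placebo, Fisher's exact test gives p = 0.052 for 5 versus 0 and p = 0.024 for 6 versus 0. A few late events would therefore be read descriptively under any reading.

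**What to change.** Keep last dose plus 7 days as the main treatment-emergent window. In the Data Analyses section of Aim 2:

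1. State that the serious-event summary includes, by arm, every serious event through Day 28 whatever its timing, as an exception to the treatment-emergent rule.
2. Give the worsening criterion the same 7-day extension after the last dose that onset and recurrence have.
3. Add a by-arm column for all reported events over Days 0-28 beside the treatment-emergent column, and state that the Chi-square or Fisher comparison is given for both event sets. This also settles what the sentence on the frequency of all reported events means.

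The cost is an edited definition, one exception and one extra column. No new visits, data or subjects are needed, and the primary analysis is untouched. The downside is a few unrelated background events in the Day 0-28 column. Keeping the treatment-emergent column separate prevents them from diluting the main view.

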We have several secondary hypotheses: a) decolonization of oropharyngeal *S. aureus* colonization with 0.12% CHG will be sustained at 28 days; b) recolonization of the oropharynx will come from isolates that colonize patients nose and not from development of antimicrobial resistance, including the emergence of CHG-resistant *S. aureus* strains that contain the *qac A/B* genes; and c) predictors of failure to decolonize with CHG will include poor treatment adherence, nasal *S. aureus* colonization, and younger age.

If our primary hypothesis is correct, findings will form the foundation for a larger, randomized, prospective, multi-center, placebo-controlled clinical trial comparing skin, nasal, and oropharyngeal decolonization vs. standard of care decolonization regimen for the prevention of recurrent *S. aureus* skin infections. If oral CHG rinse is unable to decolonize the oropharynx, then other more aggressive oropharyngeal *S. aureus* colonization eradication strategies in children will need to be tested.

B. Specific Aim(s) of the Project

1) Determine the efficacy of oropharyngeal decolonization among children with a history of CA-MRSA, CA-*S. aureus* or skin and soft tissue infection (SSTI). To determine if oropharyngeal *S. aureus* colonization can be eradicated, we will perform a randomized, double blind placebo-controlled controlled clinical trial comparing 0.12% oral chlorhexidine (CHG) oral rinse to placebo among children age 5-17 with *S. aureus* oropharyngeal colonization. We hypothesize that 0.12% CHG rinse will reduce oral *S. aureus* colonization better than placebo treatment. Our findings will provide “proof of principle” data on the ability of oral antiseptics to eradicate oropharyngeal *S. aureus* colonization in children.

2) Assess the safety, tolerability, and compliance of oropharyngeal decolonization among children and their caregivers. Using a structured instrument, we will survey trial participants and their parents/guardians on side effects, tolerability, and adherence of the 0.12% oral CHG rinse and placebo. Findings will serve as a counterpoint to any benefits derived from oral decolonization.

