Subjects randomized to oral CHG will be provided verbal and written instruction on use of CHG oral rinse. Subjects will be asked to use CHG oral rinse twice daily for 7 days. Subjects will be educated to rinse their mouth and gargle with CHG oral rinse for 60 seconds twice a day. Subjects will be instructed to use a watch or other timing device (e.g., smartphone) to ensure that at least 60 seconds have elapses. Research staff will demonstrate the technique for all subjects using drinking water. All subjects randomized to the CHG arm will be provided a new soft bristle toothbrush to prevent recontamination of the oropharynx with *S. aureus* from a contaminated toothbrush. Subjects randomized to usual care will not be provided with any of the above. Regardless of treatment allocation, study staff will educate all subjects' parent/guardian, and subject (if of sufficient age) with the clinical significance of the results of their positive test for oropharyngeal

S. aureus colonization. More specifically, they will be educated that currently testing for *S. aureus* oropharyngeal colonization is considered experimental and that if the test is positive, the clinical significance is unclear. They will also be educated that tens of millions, perhaps over 100 million Americans are colonized in the throat with *S. aureus*, and the vast majority do not suffer consequences of having this bacteria reside in the throat. Upon request, subjects will be provided with a written copy of their results as well as a written description of the clinical significance of oropharyngeal colonization that they can share with their provider, if they wish. All subjects, regardless of treatment allocation, will be provided written and verbal information about *S. aureus* and skin infection prevention and recognition of early disease. These materials were developed for previous studies done by our group.¹⁸

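### Serious and rinse-related adverse events that start after about Day 14 are collected to Day 28 but not counted by arm in the serious and related event tables

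*Combined protocol and SAP*

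**What the plan says.** **Course and follow-up.** The Baseline visit section sets the course: "Subjects will be asked to use CHG oral rinse twice daily for 7 days". Randomised children are followed for 28 days, with visits on Day 7 (Visit 2) and Day 28 (Visit 3). Under Follow-up visits, adverse events are recorded at every follow-up visit, planned or not. The Human Subjects section adds: "The survey administered at Visit 3 will collect information about (late) adverse events".

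**Treatment-emergent rule (Aim 2, Data Analyses).** The first criterion, for a new event, reads in part: "onset occurs during exposure to study medication or within 7 days after the last dose of study medication, having been absent prior to receiving study". An event that had stopped and comes back is given the same window. For a continuous event the criterion is "worsening in severity occurs during exposure to study medication relative to the pre-treatment state, when the adverse event is continuous", with no days added after the last dose.

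**Tables (same section).** All reported events go into a by-subject listing, and a second listing is sorted by MedDRA System Organ Class and Preferred Term. For tabulation the rule is "Only treatment-emergent adverse events will be included in summary tables". The named tables cover events by severity and relationship, related events, and "Summary of Serious adverse events". None carries an exception.

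**Two sentences that could be read more widely.** The sentence after the restriction promises the incidence of treatment-emergent events and also a frequency of all events reported. After the list of tables, the plan compares between groups the percentage of subjects reporting adverse events, without saying whether this means treatment-emergent events or all events.

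**Purpose.** Specific Aim 2 says of the safety results: "Findings will serve as a counterpoint to any benefits derived from oral decolonization".

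**The concern.** The plan follows each child to Day 28 and asks about harm throughout, but its serious and related event tables stop admitting new or recurring events about halfway. Taken literally, a child hospitalised for an event that began on Day 20 is absent from the serious event table. An event that began on Day 17 and was judged related to the rinse is absent from the related event table.

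The cut-off also moves with the last dose. The monitoring paragraph under Aim 1 has children who report treatment-related events discontinue the rinse, so children who react to it have the shortest tabulated follow-up. If stopping were more common in one arm, the length of tabulated follow-up would differ between arms.

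What is at stake is the comparison that Aim 2 is meant to support. Eradication is assessed to Day 28 as a secondary outcome, while serious and related harm would be counted by arm only to about Day 14.

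**Working it through.** The plan gives no figure to reproduce here. The check is date arithmetic plus a reading of which outputs the restriction reaches.

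**1. Inputs.** Course of 7 days (Baseline visit). Tail of 7 days after the last dose for new and recurring events (Aim 2, Data Analyses). Follow-up of 28 days (Inclusion and Exclusion criteria; Human Subjects). The plan does not say whether the first rinse is on Day 0 or Day 1, so the last dose of a full course falls on Day 6 or Day 7.

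**2. Formulas.** With L the day of the last dose, the window closes on day L + 7. Uncovered days = 28 − (L + 7). Uncovered share = uncovered days / 28.

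| Child | L | Window closes | Uncovered days | Share of 28 days |
|---|---|---|---|---|
| Completer, first rinse Day 1 | 7 | Day 14 | 14 | 50% |
| Completer, first rinse Day 0 | 6 | Day 13 | 15 | 54% |
| Stops on Day 3 | 3 | Day 10 | 18 | 64% |
| Stops on Day 2 | 2 | Day 9 | 19 | 68% |

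The rule uses onset date. An event first mentioned at Visit 3 that began by Day 13 or 14 is still tabulated. The shares are of follow-up time, not of events.

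**3. Where a serious or related event with onset on Day 20 would appear (completer).**

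| Output | Included? |
|---|---|
| Serious and related event tables | No: they are summary tables and no exception is stated |
| By-subject listing | Yes, expressly |
| System Organ Class / Preferred Term listing | Yes: not limited to treatment-emergent events |
| Monthly monitoring summaries of adverse and serious adverse events | Yes: not limited to treatment-emergent events, but these are monitoring reports and are not described as by-arm analyses |
| Frequency of all events reported | Unclear: it may mean a count that includes late events, which would conflict with the sentence before it, or event counts as opposed to subject counts |
| Between-arm comparison of subjects with adverse events | Unclear: the event set is not specified |

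**4. Result.** Exclusion from the serious and related tables follows directly from the text. Exclusion from the last two outputs does not.

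**The case against.** A treatment-emergent window with a tail as long as the course itself is a deliberate and ordinary choice. Late events are neither lost nor hidden from safety oversight: they are in both listings and in the monthly summaries. With 60 randomised children, a late serious event can be found by reading a listing. Such events may also be rare, since the exclusion criteria remove children with planned or likely hospitalisation in the next 28 days. The known effects of the rinse are described as transient, reversible or preventable, and no onset times are given.

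Most of this stands, and it limits the point to tabulation. It does not remove the point, because a listing gives no incidence by arm, and an event judged related to the rinse is still barred from the related table by its date.

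Four stronger readings are tempting and are not supported:

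- *Late events are missing from all safety output.* The listings and monitoring summaries include them, and two further outputs are ambiguous.
- *Visit 3 contradicts the rule.* Visit 2 is on Day 7, so Visit 3 is the first scheduled visit able to record events from Days 8 to 14, which are inside the window. Its reference to late events is compatible with the rule.
- *The between-arm comparison loses power.* The comparison sentence is not limited to treatment-emergent events. Any power figure would also need event rates and onset times that the documents do not give.
- *The rinse will look safer than it is.* That requires late onsets to be more frequent with chlorhexidine. Nothing in the documents shows this, and background illness after Day 14 should fall on both arms alike.

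**Conclusion.** The point holds as a gap in tabulation. New or recurring serious and related events that start after Day 13 or 14 in a completer, or earlier in a child who stops early, are collected but not counted by arm in the serious and related tables. The gap covers 50% to 54% of follow-up time for completers and more for early stoppers (68% if the last dose is on Day 2). It rests on reading the restriction as written, with no unstated exception for those two tables.

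Whether late events are counted by arm anywhere else is unclear, because the overall-frequency phrase and the between-arm comparison can each be read two ways. The number of events affected, and any effect on the comparison of arms, cannot be determined from the documents. The 50% to 54% should not be read as a share of events missed. No primary or secondary efficacy result, sample size or significance level is touched. This is an inexpensive improvement to the reporting plan.

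**What to change.** In Aim 2, Data Analyses, qualify the restriction on summary tables with wording such as:

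> The serious and related adverse event tables include all events with onset or recurrence from the first rinse through Day 28, by assigned arm and regardless of when the rinse was stopped. Treatment-emergent versions of these tables are presented alongside. The between-arm comparison of the percentage of subjects with adverse events is given for all events to Day 28 and for treatment-emergent events.

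In the same edit, say what the frequency of all reported events means: whether it includes events outside the window, or refers to event counts as distinct from subject counts.

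The cost is a few sentences and one more set of tables from data already collected, with no change to visits, treatment or sample size. The downside is that events from Days 15 to 28 will include background illness unrelated to the rinse. The relationship classification and the retained treatment-emergent tables let a reader separate it.
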